8.7 DATA ANALYSIS

The analysis will be cross-sectional and descriptive. Categorical data will be summarized by counts and percentages. Continuous data will be summarized using number, median, minimum and maximum values. Missing data will be noted for each variable.

A **positive outcome** reported across key pre-defined questions for each of these objectives would support the effectiveness of the educational material. For this assessment, a positive outcome is defined as at >70% of the survey participants providing a ‘correct’ response (specific questions and responses are outlined in Tables [Table 8](#) and [Table 9](#)). The 70% cut point is based on previous experience from other surveys evaluating the effectiveness of educational materials.

Table 8 - Questions to assess effectiveness in HCP survey

Category of assessment	Question text [Answer options]	Criteria for 'effective assessment'
To assess if materials are being received and read	A2. Which of the following material have you received or had access to? Select all that apply 1. Summary of Product Characteristics (SMPC) 2. Fabrazyme Home Infusion Therapy: A guide for Healthcare professionals treating patients with Fabry disease 3. Fabrazyme Home Infusion Therapy: Manual for Patients with Fabry disease who receive home infusion of Fabrazyme 4. None of the above	Majority of HCPs selecting Code 2
	A3. Have you read the Fabrazyme (agalsidase beta) home infusion educational materials? 1. Yes 2. No	Majority of HCPs selecting Code 1
To assess evaluation of home infusion	B1. Do you use the educational materials to evaluate and select patients for home infusions? 1. Yes 2. No	Majority of HCPs selecting Code 1
	B2. Which of the following criteria must be fulfilled before a patient is deemed eligible for Fabrazyme (agalsidase beta) home infusion? Select all that apply 1. Patient must be medically stable 2. A comprehensive evaluation must be completed before deciding on transfer of therapy to home infusion 3. Patient must have received Fabrazyme infusions for several months in a controlled setting and previous infusions well tolerated 4. Don't know	Majority of HCPs selecting codes 1, 2 and 3
To assess level of training to patients/caregivers	B4. Do you use the Fabrazyme (agalsidase beta) home infusion educational materials when training the patient/caregiver on the home infusion process? 1. Yes 2. No	Majority of HCPs selecting Code 1

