	
A5. How often do you [or the patient] refer to the educational materials when the home infusions are being done?
 
1. At every infusion
 
2. Frequently
 
3. Rarely
 
4. Never
	Majority of patients selecting Code 1 or 2
To assess knowledge on preparation of infusion	
B3. Which of the following statements are true in relation to the preparation, administration and storage of Fabrazyme. Select all that apply
 
1. The vials must be removed from the refrigerator approximately 30 mins before preparation
 
2. The reconstituted mixture should be shaken up
 
3. The reconstituted solution must be clear and colourless before use
	Majority of patients selecting Code 1, 3 & 4

	
4. The tourniquet should be applied to identify a vein
 
5. The product can be stored at room temperature for 48 hours before use
 
6. None of the above are true
 
7. N/A I don't prepare the infusion on my own
	
To assess knowledge on actions taken in case of AE	
C5. What would you do if [you / the patient] developed a headache and a fever during the infusion?
 
1. Complete the infusion and then rest
 
2. Immediately stop the infusion
 
3. Contact the physician
 
4. Record details in the logbook
 
5. Don't Know
	Majority of patients selecting Code 2, 3 and 4
To assess implementation of logbook	
C1. Considering the Fabrazyme (agalsidase beta) home infusion, how often do you or the nurse who helps you with the infusion (if applicable) do the following actions?
 
[1. Always / 2. Regularly / 3. Rarely / 4. Never]
 
a. Fill out the infusion data in the logbook
 
b. Take the logbook to each appointment with the prescribing physician
	Majority of patients selecting codes 1 & 2 for both actions
	
C2. How often do you or the nurse who helps you with the infusion report changes about the infusion (dose or infusion rate) in [your / the patient's] logbook?
 
1. Always
 
2. Regularly
 
3. Rarely
 
4. Never
 
5. N/A There have been no changes
	Majority of patients selecting codes 1 or 2 (excluding those selecting code 5 from calculation)
	
C6. If [you / the patient] had a side effect, should you report the side effect in your log book?
 
1. Yes, always
 
2. Only if I think it's serious
 
3. No, it is not necessary
	Majority of patients selecting codes 1

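### The Table 9 keys for patient items B3 and C5 do not say that ticking a non-keyed option makes a response incorrect, so the percentage correct can be overstated

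*Protocol*

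**What the plan says.** Protocol section 8.7 sets the success rule: "a positive outcome is defined as at >70% of the survey participants" giving a correct response, with the questions and qualifying answers set out in Table 8 (HCPs) and Table 9 (patients and caregivers). The answer key is therefore fixed in the protocol.

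Two rows of Table 9 are labelled as assessing knowledge:

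- **B3** is a multiple-response item: "Which of the following statements are true in relation to the preparation, administration and storage of Fabrazyme. Select all that apply". Its key is "Majority of patients selecting Code 1, 3 & 4". The options outside the key include code 2, "The reconstituted mixture should be shaken up", and code 5, "The product can be stored at room temperature for 48 hours before use". Code 6 says that none of the statements is true, and code 7 is a not-applicable answer for people who do not prepare the infusion on their own.
- **C5** asks what the respondent would do if a headache and fever developed during the infusion. Its key is "Majority of patients selecting Code 2, 3 and 4". Code 2 is "Immediately stop the infusion". Outside the key are code 1, "Complete the infusion and then rest", and code 5, a don't-know answer. Table 9 prints no multiple-response instruction for C5, but a three-code key can be met only if several options may be ticked.

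Neither key contains the word 'only', and nothing else in section 8.7 says what happens to a response that includes a non-keyed code.

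**The concern.** A multiple-response knowledge item separates informed from uninformed respondents partly through its wrong options. If the score depends only on whether the keyed codes are ticked, the wrong options have no effect. A respondent who ticks B3 codes 1 to 5 meets the key, and so does one who ticks C5 codes 1 to 4.

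B3 and C5 are the only Table 9 rows labelled as knowledge, and knowledge of the key content areas is part of the primary objective (section 7). Scoring without regard to the non-keyed options can never give a lower percentage than exact-set scoring, so any error favours a positive outcome. Because the key can be read either way, two analysts could also score the same responses differently and reach opposite conclusions on an item.

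**Working it through.** **Inputs from the protocol.** The patient sample is n = 18 (section 8.5.2), the threshold is more than 70% correct (section 8.7), and the keys are those in Table 9.

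**Reproducing the plan's own figures.** Table 7 gives precision for n = 18. The half-width 1.96 × √(p(1−p)/18) gives:

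| p | Recomputed (points) | Table 7 |
|---|---|---|
| 0.80 | 18.48 | 18.5 |
| 0.75 | 20.00 | 20.0 |
| 0.70 | 21.17 | 21.2 |
| 0.60 | 22.63 | 22.6 |

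Table 7 reproduces. The point concerns the scoring rule and disputes none of these figures.

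**Pass mark.** The smallest k with k/18 > 0.70 is 13: 12/18 = 66.7% and 13/18 = 72.2%. Suppose 13 patients tick all keyed codes and one of them also ticks a non-keyed code. Under the key as written the item scores 13/18 and is positive. Under exact-set scoring it is 12/18 and is not.

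**Chance of a positive item.** Let p be the probability that a respondent ticks all keyed codes, and f the share of those who also tick a non-keyed code. Then

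- key as written: P(Bin(18, p) ≥ 13);
- exact set: P(Bin(18, p(1−f)) ≥ 13).

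The documents give neither p nor f, so all values below are assumptions. The calculation also treats respondents as independent and keeps all 18 in the denominator.

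| p | As written | f = 5% | f = 10% | f = 20% |
|---|---|---|---|---|
| 0.70 | 0.534 | 0.406 | 0.291 | 0.124 |
| 0.80 | 0.867 | 0.751 | 0.609 | 0.322 |
| 0.90 | 0.994 | 0.964 | 0.890 | 0.609 |

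For p = 0.80, the exact-set probabilities are 0.80 × 0.95 = 0.76, 0.80 × 0.90 = 0.72 and 0.80 × 0.80 = 0.64.

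**How the key reads beside other rows.** Patient item A2 is also multiple-response and its key uses the same form of words for code 2. There the wording must be inclusive, because having the package leaflet as well cannot cancel receipt of the manual. The only exclusion written into a Table 9 key is for item C2, where the not-applicable code is removed from the calculation. No comparable words appear for B3 or C5.

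**The case against.** **Exact-set scoring may be what the authors meant.** A reader might infer that the protocol expressly accepts wrong answers as correct. It does not: it is silent on extra codes. For a question asking which statements are true, a list of three codes can naturally be read as the complete answer. The column is also loosely worded. On single-choice frequency scales (HCP B5, C1, C2 and C4; patient C1) the ampersand between codes 1 and 2 can only mean 'or'. A2, the inclusive comparator, has no false statements among its options, so its reading need not carry over to a knowledge item. This stands, and it makes the finding an ambiguity with a one-sided risk, not a declared scoring error.

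**Survey logic or a later document may settle it.** Section 8.8.1 describes live prompts for illogical answers and says that the checks are specified in the data collection materials, which are not shown here. A prompt could catch C5 codes 1 and 2 ticked together. It need not catch B3 codes 2 or 5, because a false belief is not a logical conflict. An analysis plan could also state the rule, but section 8.7 places the definition of a correct response in the protocol's own tables.

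**C5 is the weaker case.** Its codes 1 and 2 conflict. Someone who would complete the infusion would usually leave code 2 unticked and so already fails the key. It would be too strong to infer that every mistaken patient is counted as a success. Only those who tick all the keyed codes and a wrong one are affected.

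**The size is not known.** It is tempting to quote a single dramatic contrast. With 60% fully correct and a further 15% adding a wrong code, the chance of a positive item is 0.21 under exact-set scoring and 0.72 as written. That arithmetic is right, but it assumes that one key-ticker in five (0.15/0.75) over-ticks. No figure in the documents supports that share, so only a range is defensible.

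**The consequence is limited.** The analysis is descriptive, and support for effectiveness rests on several key questions. Section 11.2 asks for the results to be read together with safety and clinical outcomes. Per-option counts are in effect already planned, so over-ticking would be visible. None of this settles which answer counts as correct.

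**Conclusion.** The concern holds as an incompletely specified key. Applied literally, the Table 9 criteria for B3 and C5 leave the non-keyed options without effect, and the percentage correct can only be raised. The realistic exposure is B3 codes 2 and 5; C5 code 1 is less likely to matter.

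At n = 18, one respondent can decide an item. Under the assumed p = 0.80, the literal key raises the chance of a positive item by 0.12, 0.26 or 0.55 (0.867 minus 0.751, 0.609 or 0.322) as f goes from 5% to 10% to 20%. These differences rest wholly on assumed shares. The documents do not support saying that the survey's overall conclusion would be reversed. The point deserves correction because it touches the only two patient items labelled as knowledge and costs almost nothing to settle in advance.

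**What to change.** State in the criteria column of Table 9 that a response is correct only if it is exactly the keyed set:

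- **B3:** codes 1, 3 and 4 selected, and none of 2, 5, 6 or 7.
- **C5:** codes 2, 3 and 4 selected, and neither 1 nor 5.

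Apply the same scoring principle to HCP item B6 in Table 8, whose key names codes 1 and 3 and is likewise silent on the others. The principle is applied against the sponsor's own keys and takes no view on which clinical action is right.

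The cost is a few words in two tables, with no change to the questionnaire, the sample or the threshold. The downside for the sponsor is that the percentage correct can only stay the same or fall.

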7 RESEARCH QUESTION AND OBJECTIVES

The overall objective of this survey study is to assess the effectiveness of the education materials for home infusion therapy from both the HCP and the patient /caregivers perspectives. Effectiveness will be measured through questions on knowledge and understanding of key content areas. Implementation of the logbook around the key content areas will also be used to assess effectiveness of the materials s

- The primary objective is to determine effectiveness of the educational materials through questions measuring :
 - The level of knowledge and understanding regarding key content areas of the educational materials including:
 - Evaluation of home infusion (HCP)
 - Elements to address when training the patient/caregiver
 - Actions to be taken in case of an adverse event
 - Implementation of the logbook (owned by the patient but reviewed by the HCP)

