8.3.4 Patient Survey Questionnaire

Upon informed consent from the patient, eligible patients will be passed a link to access and complete the main survey. Data will be entered online independently by the patient. All data entered will be captured on the online server to be downloaded at the end of fieldwork.

Table 5 - Overview of patient main survey questions*

Section	Content
Section 1	Key performance indicators 
 • Materials provided by physician • Which materials were received • Have materials been read • Involvement of infusion nurse or other medical trained professional • Frequency in which materials are referenced
Section 2	Understanding and knowledge of educational materials 
 • Overall usefulness rating of materials • Ease of understanding of the key sections in education materials • Knowledge assessment of preparation, administration and storage of Fabrazyme • Frequency key preparation and administration steps conducted
Section 3	Implementation of the logbook and handling AR 
 • Frequency in which logbook is completed and taken to appointments • Frequency Infusion changes reported in logbook • Familiarity with side effects/risks associated with home infusion • Sources of information for learning about side effects/risks • Action taken in case of AR (knowledge assessment) • Reporting side effects in logbook • Frequency logbook discussed with physician • Usefulness of logbook • Sources of information for home infusion

*content included, but not limited to items in table

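### Patient item C6 is scored as logbook implementation but asks only whether a side effect should be reported, so it measures knowledge or intention rather than what was recorded

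*Protocol*

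**What the plan says.** Section 7 of the Protocol gives two kinds of evidence for effectiveness. One is knowledge and understanding of key content areas. The other is listed separately as "Implementation of the logbook (owned by the patient but reviewed by the HCP", and the same section adds that "Implementation of the logbook around the key content areas will also be used to assess effectiveness of the materials".

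Table 9 in Section 8.7 follows that division for patients and caregivers, with rows for knowledge and a row headed "To assess implementation of logbook". The last contains C1, C2, C6 and C7. C6 asks: "C6. If [you / the patient] had a side effect, should you report the side effect in your log book". The three options are that one should always report it, "Only if I think it's serious", or that it is not needed. The criterion is "Majority of patients selecting codes 1".

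Section 8.7 sets the pass rule: "a positive outcome is defined as at >70% of the survey participants providing a ‘correct’ response". It applies this across the pre-defined questions for each objective. In the questionnaire outline (Section 8.3.4, Table 5) the topic appears as "Reporting side effects in logbook", without the knowledge-assessment label that the outline gives to the item on action in case of an adverse reaction.

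**The concern.** C6 is conditional (if there were a side effect) and normative (should you report it). A respondent can answer it correctly without ever having had a side effect, or having had several and recorded none. Under Table 9 that answer is counted as evidence that the logbook is being used.

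The Protocol keeps knowledge and logbook implementation apart and judges a positive outcome for each objective, so the category in which C6 sits affects what can be concluded. A pass on C6 would be reported as implementation when it shows only what respondents believe they ought to do. Recording of side effects is a safety-relevant use of the logbook, so the distinction matters to a regulator reading the result.

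**Working it through.** The point turns on wording and classification, so the check sets the items side by side.

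**Patient items scored as logbook implementation (Table 9)**
- C1a: how often infusion data are filled in. Behaviour, frequency scale.
- C1b: how often the logbook is taken to appointments. Behaviour, frequency scale.
- C2: how often changes of dose or infusion rate are reported. Behaviour, frequency scale, with those who had no changes excluded from the calculation.
- C6: whether a side effect should be reported. Belief or intention, with no frequency scale and no option for having had no side effect.
- C7: how often the logbook is reviewed with the physician. Behaviour, frequency scale.

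**HCP items scored as logbook implementation (Table 8)**
- C1, C2 and C4a to C4d all ask how often something is done.

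C6 is therefore the only logbook item in either table that asks what should be done.

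**Items of the same form as C6**
- Patient C5 asks what the respondent would do if symptoms developed during the infusion. It is scored as knowledge.
- HCP B6 asks which steps should be taken after an infusion associated reaction. It is scored as knowledge.

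By the Protocol's own practice, a question in the form of C6 belongs with knowledge.

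**Does another scored item cover actual recording of side effects?** C1a concerns infusion data, C2 dose or rate changes, and C7 review with the physician. Code 4 of C5 mentions entering details in the logbook, but C5 is hypothetical and scored as knowledge. Table 3 lists an HCP topic on action when reactions are found in the logbook, but Table 8 does not score it. No scored item in either table asks whether side effects that occurred were recorded.

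**What a pass requires.** Inputs: 18 respondents (Section 8.5.2), all answering, and the 70% rule (Section 8.7). 12/18 = 66.7% fails and 13/18 = 72.2% passes, so 13 answers of code 1 are enough. If the word majority in the criterion were read as more than 50%, 10/18 = 55.6% would be enough. Under either reading the number of side effects actually recorded does not enter the rule, and 18/18 correct is compatible with no entries at all.

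**Figures in the plan.** The precision figures for n = 18 in Table 7 reproduce with the usual normal approximation. At 70%, 1.96 × √(0.7 × 0.3 / 18) = 21.2 percentage points, as printed. They do not depend on how C6 is classified.

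**The case against.** The strongest reply is that this is only a label. Knowledge and logbook implementation both feed one assessment of effectiveness, C6 is scored as its own row, and moving it changes the heading but not its percentage. Table 5 also groups the topic under a combined section on the logbook and handling of adverse reactions, where a hypothetical item is at home. The percentage would indeed not change. But Section 8.7 judges the outcome for each objective and Section 7 lists the two separately, so the heading decides which objective the percentage supports. The reply fails on that point.

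Other parts of the reply stand:
- A reader might infer that part of the primary objective goes unanswered. The Protocol states no sub-objective on recording side effects, and C1, C2 and C7, with the HCP items, still measure logbook behaviour.
- A reader might want a pass probability attached to C6. Any such figure would rest on an assumed share of correct answers and would be the same for every single-answer item with 18 respondents, so it says nothing about the misclassification.
- A reader might call the item leading, or fault it for lacking a don't-know option. Two of the three options are plausible incorrect answers, and knowledge item B3 has no don't-know option either. The charge is not shown.
- Rewording C6 as behaviour would not be free. Section 6.1 says home infusion is considered for patients who tolerate infusions well, so few may have had a side effect. The Protocol gives no rate. If 20% to 40% of 18 had one (an assumption), 3.6 to 7.2, or about 4 to 7, would remain. Section 10 also says the study is not designed to collect individual adverse drug reactions. A hypothetical item that all 18 can answer is a defensible choice, provided it is scored as what it is.
- The full patient questionnaire (Appendix 2) is not shown and may hold an unscored behavioural item. That would not alter the scoring in Table 9.

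**Conclusion.** The point holds at item level. C6 measures knowledge or intention and is counted as logbook implementation, and it can pass whatever was actually recorded. It affects one of four patient logbook items, so it weakens the logbook assessment without voiding it. No scored item measures actual recording of side effects, and a pass on C6 should not be read as showing it. No sample-size, precision or error-rate figure is affected. The conclusion rests on the printed wording and scoring in Tables 8 and 9, and assumes that C1a, on infusion data, does not include reactions, which the Protocol does not define.

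**What to change.** Before fieldwork, move C6 in Table 9 to the knowledge category on actions in case of an adverse event, beside C5, and do not count it towards logbook implementation. Note there that it overlaps with code 4 of C5, so that the two are not presented as independent evidence. Mark the topic as a knowledge assessment in Table 5. State in the report that side-effect recording behaviour was not assessed. The cost is one table row and one sentence; the question itself need not change.

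Optionally, add a behavioural item on the pattern of C2: how often side effects that occurred were entered in the logbook, with answers Always, Regularly, Rarely, Never, and not applicable because there were none, the last excluded from the calculation. Report it descriptively only and without the 70% rule, because its denominator may be very small. The cost is one extra question, and its wording should be checked against the adverse-reaction reporting arrangements in Section 10.

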8.8 QUALITY CONTROL

Standard operating procedures will be applied to ensure quality to all aspects of the survey conduct, data management and analysis.

8.8.1 Data quality management

To ensure the validity of the results, it is necessary to ensure that the data collected are of good quality. This implies minimizing any missing data and ensuring the data collected is accurate. To maximize data quality, the following procedures will be undertaken:

1. Adelphi will thoroughly brief local fieldwork agencies, detailing study objectives, physician inclusion criteria and other logistical aspects of the study. Adelphi will also carry out regular follow-up by telephone/email to ensure the physician screening and recruitment is being executed correctly.
2. Both the screener and questionnaire will be carefully designed to contain clear respondent instructions at each question.
3. The survey will primarily consist of questions that include a list of predefined answers for participants to select from when making their responses.
4. Logic checks will be programmed in the internet script to define expected ranges/answers, based on research team's experience and therapeutic knowledge. The online link will also contain "live" checks and error messages to prompt the physician to check missing data and illogical answers whilst they are completing the survey.
 - 4.1 All logic checks are specified in the data collection materials that are supplied; the script writer programs the logic checks and the research team checks that the logic is implemented before fieldwork.
5. The patient/caregiver survey will be piloted by 1 patient/caregiver per country in advance of main fieldwork to check the design and language used in the survey is understandable and that all survey logic is implemented.
 - 5.1 The patient/caregiver will complete the online survey and then participate in a telephone debrief with a research team member commenting on any issues in the survey.
 - 5.2 Research team member will review the data downloaded from the survey to ensure all logic is correct.
 - 5.3 Any changes suggested will be recorded in an 'internet checking log' and the scriptwriter indicates whether and when each change is actioned.
 - 5.4 This is incorporated into the patient survey prior to main fieldwork.
 - 5.5 To ensure we do not jeopardize patient recruitment we will target a patient with a similar condition to Fabry for doing the pilot interview.
6. The survey will be soft-launched. 1 HCP and 1 patient/caregiver in each country will be fielded before full launch of fieldwork. This will check that the design of the questionnaire works in practice.
 - 6.1 The respondents complete the online survey

6.2 Research team member will review the data downloaded from the survey to ensure all logic is correct.

6.3 Any errors found will be recorded in the 'internet checking log' and the scriptwriter indicates whether and when the change is actioned.

6.4 Changes are then tested by the researcher and uploaded to the main survey link for main fieldwork.

6.5 Adelphi will perform quality control checks once in field to ensure data integrity and will follow quality control guidance. Checks include: repeated response patterns, straight-lined responses through rating scale questions and high speed completion of survey (See appendix for Data quality control document)

6.5.1 Data is downloaded, checked and flagged in fieldwork monitoring report that is sent to researchers daily.

6.5.2 Research team review the flagged respondents and exclude the respondent data if the data is suspect.

6.5.3 Fieldwork agency is notified that this respondent will need to be replaced and reason for exclusion.

7. All data collection material will be translated to the required languages by selected agencies / approved translators. Translated materials will be sent to members of the freelance proof-reader team, who will check the final translated web interface for accuracy.

